5.4 Data Management for WP3

For WP 3, linking the CRF data and the NHS Thermometer data by patient identifiable data will be done by the research team at the site. Participants will be allocated the same study identifier in both data sets. The data set will be anonymised before secure transfer from site to the University of Warwick according to WCTU SOPs. A record of participant study number and NHS number used to link the participant to the study will be kept in a locked cabinet at the research site until data is locked for analysis at the end of the study or according to local research SOPs before being destroyed.

5.5 Data Analysis for WP3

Descriptive statistics will be used to summarise patient characteristics and outcomes according to patient personal preference, ReSPECT clinical treatment recommendation and resuscitation status. We will use appropriate multiple regression techniques to explore the associations between patient characteristics, resuscitation status (DNACPR or for resuscitation), care group and risk of harm and death. Firstly, by fitting a series of nested models with DNACPR (yes/no) as the dependent variable and patient characteristics and clinical treatment recommendation as indicated on the ReSPECT form) as the independent variables we will assess the influence of patient characteristics at baseline and patient preference on DNACPR decision and establish whether the patient preference adds information beyond that provided by the patient characteristics as regards the DNACPR decision. Secondly, we will use ordered logistic regression with care group ('Focus on Life-Sustaining Treatment' and 'Focus on Symptom Control' and 'No Decision') as the dependent variable and patient characteristics as the independent variables to assess whether patient characteristics influence the choice of care group. Finally, we will use logistic regression (conditional should we be able to match cases to controls), with and without adjustment for patient characteristics, with harm (yes/no, obtained from the NHS Safety Thermometer) as the dependent variable and care group ('Focus on LifeSustaining Treatment' and 'Focus on Symptom Control') and DNACPR (yes/no) as independent variables to assess whether focus of care group or DNACPR order independently influence risk of harm.

Sample size: As this is an exploratory analysis a formal sample size calculation is not appropriate.

Nevertheless, for generalisability we need to ensure a reasonable spread of patients/decisions, and in order to model risk of harm we need sufficient harmful events to have occurred. Based on our pilot data we expect 70% of patients to have a ReSPECT decision, of whom 20% will have a DNACPR decision. 20-30% will have no decision, which by default means they would receive resuscitation in the event of cardiac arrest. We therefore intend to enrol 3000 patients in this study (minimum 500 patients per site, six sites). Assuming a "harm rate" of 6.5% (based on 2014 NHS Thermometer data), this will provide 200 incidences of harm for the risk modelling. If possible, for the modelling of harms, we will match cases to controls in order to increase statistical power.

6. WORK PACKAGE 4 - FOCUS GROUPS WITH GENERAL PRACTITIONERS, COLLECTION OF CONTEXTUAL DATA ON IMPLEMENTATION AT SITES, SYNTHESIS OF FINDINGS AND IDENTIFICATION OF AREAS FOR IMPROVEMENT AND FURTHER WORK

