A member of the site research team will create a list of patients with a ReSPECT form completed or validated during this admission. They may use their hospital system, if their system records ReSPECT form completion, to extract a list of patients on the ward(s) where clinician observations have been conducted or they will ask the lead nurse for a locally held list. If they are unable to create a list in either of these ways, a member of the site research team will screen patient records on the ward(s) to identify patients with a ReSPECT form completed or validated during this admission. Patients admitted with ReSPECT forms completed in community settings (e.g. by a GP), will be noted on the list. The site research team will also

make a record if there is documentation in the patient records stating the patient lacks capacity to the extent they could not consent to take part in a research interview.

The researcher conducting the interviews will identify potential participants (either patients or family members for those unable to give consent) based on the purposive sampling frame developed for WP1a. Prior to approaching any identified patients, the researcher will consult with the clinical staff to check whether the patient is well enough to be approached and whether they have capacity to give informed consent to take part. If they do not have capacity, the researcher will ask the clinician to approach a family member, if available. The clinician will ask the patient or family member if they are willing for the researcher to talk to them about the study. If they agree, the clinician will introduce the researcher and the researcher will give the potential participant an information sheet and arrange for the researcher conducting the interviews to return once the potential participant has had sufficient time to make an informed decision about whether or not to take part (usually 24 hours). When the researcher returns, they will first check with clinical staff that patients are well enough to discuss participation. The researcher will approach those patients who are well enough, or family members, in order to answer questions about the research and seek written informed consent should the patient or family member wish to take part.

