5.1 Study Design

Retrospective observational study

Sampling: Six acute hospitals selected for work package one

Inclusion criteria: Adult in-patients

Exclusion criteria: Paediatrics, Neonates, day case admissions, refusal of consent.

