5.1.3 Research Questions

- 1. What combinations of emergency care and treatment plans are recorded on ReSPECT. How are they related to patient characteristics and overall outcomes of patients?
- 2. Which patient characteristics predict assignment to particularly emergency care and treatment plans?
- 3. Which patient characteristics predict assignment to a DNACPR?
- 4. Do particular patient preferences and emergency care and treatment recommendations predict a DNACPR decision?
- 5. Is a DNACPR decision an independent predictor of patient harm?

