5.3 Data Collection for WP3

The following information will be extracted from the clinical and audit/or records:

(1) Demographics (age, gender, ethnicity, abbreviate home postcode as a proxy for social class), (2) Reason for admission, (3) Co-morbidities: Cognitive impairment (dementia, learning difficulties), Charlson co-morbidity index [56], GO-FAR sore [57] (both of which predict outcome from cardiac arrest), assessment of whether their condition is likely to be fatal (measured by McCabe Scale [58]), (4) ReSPECT (patient preference, emergency care treatment decisions, resuscitation status, capacity, who was involved in the discussions, when, where and by whom was the decision made), (5) NHS Safety Thermometer Audit data, (6) Length of hospital stay, survival to discharge, discharge location.

We will endeavour to ensure that researchers collect baseline data blind to ReSPECT classification. Practically what this means is that the researcher will first extract the baseline data, some of which may need some interpretation. Only when this is complete will they extract ReSPECT classification data which does not require any interpretation.

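### WP3's DNACPR and care-group models apply no timing condition, so admission-specific characteristics may be read as influencing decisions made before the admission

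*Protocol*

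**What the plan says.** The WP3 population is stated in section 5.1 as "Inclusion criteria: Adult in-patients". The listed exclusions do not concern when or where a resuscitation decision was made.

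Section 5.1.3 asks "Which patient characteristics predict assignment to a DNACPR", and puts the same question for assignment to care plans.

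Section 5.5 answers by "fitting a series of nested models with DNACPR (yes/no) as the dependent variable and patient characteristics and clinical treatment recommendation" as independent variables, and reads the result as follows: "we will assess the influence of patient characteristics at baseline and patient preference on DNACPR decision". A second model, ordered logistic regression with care group as the outcome, is likewise meant to show whether characteristics influence the choice.

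The data extracted under section 5.3 include "2) Reason for admission, (3) Co-morbidities". For the ReSPECT decision they also include "who was involved in the discussions, when, where and by whom was the decision made". No model in section 5.5 uses that timing or place.

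Section 5.3 has baseline data extracted before the ReSPECT classification. That serves blinding; it does not define baseline relative to the date of the decision.

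WP1a expects forms to arrive from outside. Its second research question (3.2.1) concerns patients who bring such a document, section 3.2.4 oversamples these cases for interview, and section 3.2.2 says "Patients admitted with ReSPECT forms completed in community settings (e.g. by a GP), will be noted on the list".

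**The concern.** To say that a characteristic predicts or influences a decision, the characteristic must come first. Reason for admission does not exist until the patient is admitted. For a patient whose form was completed in the community and left unchanged, the order is reversed: the decision is the earlier event and the admission the later one.

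A model fitted to everyone's recorded status mixes two relations. One is how the admission bears on decisions made during it. The other is how patients who already hold a decision come to be admitted, and for what. A single coefficient for an admission-specific term averages the two, and the reader cannot tell them apart. At stake are the answers to research questions 2 and 3 for those terms. The wider description of how ReSPECT is used does not depend on this.

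**Working it through.** **Inputs from the protocol.** Section 5.5: at least 500 patients at each of six sites; 70% with a ReSPECT decision, of whom 20% have a DNACPR decision; harm rate 6.5%.

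**The plan's own figure.** 6 × 500 = 3000 patients; 3000 × 0.065 = 195 harms, which agrees with the rounded 200 in section 5.5. No stated figure is in error.

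**Expected DNACPR decisions.** 3000 × 0.70 × 0.20 = 420, or 0.70 × 0.20 = 14% of patients.

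**Assumption.** The share *f* of DNACPR decisions carried in unchanged is not given, so a range is used. Affected decisions = 420 × *f*; remaining decisions = 420 × (1 − *f*).

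**Illustration of the distortion.** Take two equal-sized groups by reason for admission, with 14% DNACPR overall. Carried-in decisions make up 0.14 × *f* of all patients. Among the rest, the average in-hospital risk is *q* = 0.14(1 − *f*) / (1 − 0.14*f*).

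- Case A: the in-hospital odds ratio is 2.0, and carried-in decisions are unrelated to the reason for admission.
- Case B: the in-hospital odds ratio is 1.0, and carried-in decisions are twice as common in one group.

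Worked at *f* = 20%: carried-in = 0.028; *q* = 0.112 / 0.972 = 0.1152.

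- Case A: group risks averaging 0.1152 with odds ratio 2.0 are 0.0809 and 0.1496. Adding carried-in decisions gives 0.028 + 0.972 × 0.0809 = 0.1066 and 0.028 + 0.972 × 0.1496 = 0.1734. Pooled odds ratio = (0.1734/0.8266) / (0.1066/0.8934) = 1.76.
- Case B: carried-in shares are 0.0187 and 0.0373. Totals are 0.0187 + 0.9813 × 0.1152 = 0.1317 and 0.0373 + 0.9627 × 0.1152 = 0.1483. Pooled odds ratio = (0.1483/0.8517) / (0.1317/0.8683) = 1.15.

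| *f* (assumed) | Affected of 420 | Remaining | Case A: true 2.0, pooled | Case B: true 1.0, pooled |
|---|---|---|---|---|
| 5% | 21 | 399 | 1.94 | 1.03 |
| 10% | 42 | 378 | 1.88 | 1.07 |
| 20% | 84 | 336 | 1.76 | 1.15 |
| 30% | 126 | 294 | 1.65 | 1.23 |
| 40% | 168 | 252 | 1.54 | 1.33 |

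Pooling can dilute a real association or create a spurious one. On the log scale, case A loses 1 − ln 1.88/ln 2 = 9% of the effect at *f* = 10%, 1 − ln 1.76/ln 2 = 18% at 20%, and 1 − ln 1.65/ln 2 = 28% at 30%.

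**The case against.** The case on the other side is substantial, and several parts of it stand.

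- **Pooling is inferred.** No sentence says that pre-admission decisions will be combined with the rest; this follows from models stated without restriction. Subsetting is often left to an analysis plan. However, the only plan the protocol promises (section 4.5.1) is for the interrupted time series in WP2. For WP3, section 5.5 itself fixes the outcome and the interpretation.
- **Covariates are not named.** Section 5.5 speaks only of patient characteristics. Reason for admission appears in the extraction list in section 5.3, so the point applies to such a term if it is entered.
- **Carried-in forms may be reconsidered.** Section 3.2.2 refers to forms completed or validated in this admission, the form in Appendix 1 has a section for confirming validity, and section 2.1 expects an acute admission to prompt review. A revalidated recommendation can reflect the reason for admission. The problem is therefore confined to forms carried in unchanged.
- **The share may be small.** Section 1.1 expects most decisions, at least initially, to be taken in the acute hospital, and section 2.1 expects completion at admission.
- **WP3 is descriptive.** Its aim and section 5.5 also speak of associations, and section 5.5 calls the analysis exploratory.

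A reader might go further and infer that severity scores and laboratory values are read on the survey day, after in-hospital decisions too. The documents do not support this. Severity and laboratory results appear only as examples in section 2.3, which defers to section 5.3; that section lists neither as an item of its own and places the GO-FAR score under comorbidities. Nothing says that values are taken on the survey day. A reader might also infer that the whole set of predictors is compromised. It is not: demographic variables and long-standing comorbidity precede the decision whether it was made before or during the admission.

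**Conclusion.** The point holds in a limited form. As written, the WP3 DNACPR and care-group models take every in-patient's recorded status whatever its date, and read the coefficients as influence. For decisions carried in and not revalidated, that reading fails for admission-specific characteristics.

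The size rests on an assumed share. At 10% to 30%, 42 to 126 of about 420 DNACPR decisions are affected. The odds ratios come from a two-group illustration and are not estimates for this study; they show small distortion at about 10% and material distortion from about 20%. If nearly all carried-in forms are revalidated, or no admission-specific term is entered, the effect is negligible. Because WP3 is exploratory, the point is minor to moderate. It is still worth acting on, since the remedy relies mainly on data WP3 already extracts.

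**What to change.** In section 5.5:

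1. Use the extracted date and place of the decision to classify each decision as made or revalidated in this admission, or carried in unchanged. Say how a form is classed if its revalidation was not captured, since section 5.3 does not list revalidation separately.
2. For research questions 2 and 3, report the DNACPR and care-group predictor models for decisions made or revalidated in this admission alongside the all-decisions models. Interpret admission-specific predictors from the former only.
3. Describe carried-in decisions separately.
4. Describe the all-decisions results as associations, and change the wording on influence to match.

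Keeping the all-decisions model preserves WP3's aim of describing ReSPECT use among all in-patients.

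The cost is analysis wording, one derived variable and one further model per outcome. The restricted DNACPR model has fewer events: 378 to 294 in place of 420 at assumed shares of 10% to 30%.

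Re-dating GO-FAR, severity or laboratory values to the decision is not recommended. The timetable in section 7.5 shows WP3 data collection complete at five of six sites, so this would mean repeat extraction. Using the decision date for patients with a decision and the survey day for those without would also measure the two outcome groups at different points in their stay, which adds a bias of its own.

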Generalisability: The evaluation described in WP 1 and 3 will take place in six Acute Trusts purposely sampled for diversity according to volume of admissions, approach to ReSPECT implementation, performance according to CQC banding, and social class and ethnic mix of populations served. Work package 2 will use data from the National Cardiac Arrest Audit which has >70% national coverage. This project focuses on implementation in the acute hospital setting in the expectation that most decisions, at least initially will be taken in this setting and provide the opportunity to observe the transferability of decisions between healthcare settings.

Building on existing work: This project builds on the findings from our previous HSDR work. This identified: resuscitation is still performed where it has little or no chance of success; patient and family involvement in decision-making in DNACPR decisions is sub-optimal;

DNACPR decisions are often conflated to mean 'not for active treatment' and decisions generate ethical challenges for health care professionals at each stage in the process.

Our early pilot work explored the use of overall treatment plans and suggests they improve decision-making and patient involvement leading to better outcomes for patients. The need for ECTP with concurrent evaluation was rated as the number one research priority at the national patient, public, clinician and policy maker event we hosted in October 2014.

The project will provide an opportunity to conduct a robust prospective evaluation of a large-scale change in NHS policy and practice. It is focused on resuscitation decisions and advance care planning; providing information about the consequences of this policy change on the three main areas identified as most important by patients and clinicians and highlighted by independent enquires. We will also consider how our finding may be transferable to other initiatives and any wider uses of our methodological approaches.

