5.3.1 Outcomes

As our measure of patient harm we will use the data collected for the NHS Safety Thermometer. In participating Acute Trusts this point of care survey collects data on 100% of inpatients for one day each month. Our outcome of interest in the Classic Thermometer is 'harm free care' defined as none of the defined adverse events being present on the day of the assessment (pressure ulcers, urine infections in catheterised patients, falls, or venous thromboembolism). These are all events that would be associated with less intense care. If as a consequence of a DNACPR order, there are more of these events we will conclude that more work is needed to prevent iatrogenic harms caused by DNACPR orders leading to a lower level of care.

A second harm measure, the 'Medication Thermometer', is being rolled out in the NHS. This also a point of care survey collecting data on 100% of in-patients for one day each month. Our outcome of interest here is 'drug induced harm'. The survey identifies people who are using a specified list of high-risk medicines. There is then a discussion between a nurse, doctor and a pharmacist to assess if the patient has been harmed and the level of any harm. Harm will be defined as a moderate (or greater) incident which results in a moderate increase in treatment and which caused significant but not permanent harm. We will collect Medication Thermometer data where it is routinely available.

Standardisation of Data collection: NHS Safety Thermometer data will be extracted by NHS audit, clinical or site research staff who have been trained in the use of the tool. We are aware of variation in Thermometer measurements and will develop a training set of standardised cases in to improve consistency. We will work closely with the six sites to ensure the approach is standardised and report on reliability from the standardised cases.

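### The three WP3 regressions name no hospital term, so the DNACPR–harm odds ratio can mix differences between hospitals with the within-hospital association that research question 5 asks about

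*Protocol*

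**What the plan says.** Protocol section 5.5 writes out three regressions.

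- DNACPR model: "fitting a series of nested models with DNACPR (yes/no) as the dependent variable and patient characteristics and clinical treatment recommendation" as independent variables.
- Care-group model: an ordered logistic regression with "patient characteristics as the independent variables to assess whether patient characteristics influence the choice of care group".
- Harm model: a logistic regression "with and without adjustment for patient characteristics, with harm (yes/no, obtained from the NHS Safety Thermometer) as the dependent variable", with care group and "DNACPR (yes/no) as independent variables to assess whether focus of care group or DNACPR order independently influence risk of harm".

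No hospital indicator, random effect or stratum appears in any of them, and no other WP3 section adds one. The harm model may be "conditional should we be able to match cases to controls". The matching factors are not named, and the reason given is power: "we will match cases to controls in order to increase statistical power".

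Section 1.1 describes "six Acute Trusts purposely sampled for diversity according to volume of admissions" and, among other features, according to how ReSPECT was implemented. Section 5.3.1 says "We are aware of variation in Thermometer measurements" and answers this with a set of standardised training cases, close work with the six sites and a report on reliability. Section 8 adds training of site staff and quality checks.

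**The concern.** Research question 5 (section 5.1.3) asks whether a DNACPR decision independently predicts harm. Section 5.3.1 says in advance what will be concluded if harm events are more frequent as a consequence of DNACPR orders: that more work is needed to prevent harm caused by those orders. Only the comparison of patients inside the same hospital speaks to that question.

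Hospital can confound the comparison if two things hold together: DNACPR recommendations are more common in some hospitals than others, and recorded harm also differs between hospitals. The protocol makes both plausible through the deliberate diversity of sites (including implementation approach) and the admitted variation in the harm measure. Patient covariates can absorb differences in case mix, but not differences in how a hospital records harm or in its local habit of writing DNACPR recommendations. A pooled odds ratio could then suggest a harm that exists within no hospital, or hide one that does.

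**Working it through.** **Inputs from the protocol (section 5.5).** 3000 patients, six sites, at least 500 per site; harm rate 6.5%; 70% with a ReSPECT decision, of whom 20% have DNACPR.

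**The plan's own figure.** 3000 × 0.065 = 195 harms, which the protocol rounds to 200. It reproduces.

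**Derived.** DNACPR share 0.70 × 0.20 = 14%, or 420 patients. Per site on average: 500 × 0.14 = 70 DNACPR patients and 500 × 0.065 = 32.5 harms.

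**Assumptions.** Six sites of 500. Within each site DNACPR and harm are independent, so the true within-site odds ratio is 1. The protocol gives no site-level rates, so the spreads below are assumed; each keeps the means at 14% and 6.5%.

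- Mild: DNACPR 10, 11.5, 13, 15, 16.5, 18%; harm 4.5, 5.3, 6.1, 6.9, 7.7, 8.5%.
- Wide: DNACPR 6, 9, 12, 16, 19, 22%; harm 3, 4.5, 6, 7, 8.5, 10%.

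**Formula.** With d and h the DNACPR and harm proportions at a site, sum over sites a = 500·Σdh, b = 500·Σd(1−h), c = 500·Σ(1−d)h, e = 500·Σ(1−d)(1−h). The crude pooled odds ratio is ae/(bc).

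**Wide spread, fully aligned.** Σdh = 0.0624, so a = 31.2. Then b = 420 − 31.2 = 388.8, c = 195 − 31.2 = 163.8, e = 2580 − 163.8 = 2416.2. OR = (31.2 × 2416.2)/(388.8 × 163.8) = 1.18.

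**Wide spread, fully reversed.** Σdh = 0.0468, so a = 23.4, b = 396.6, c = 171.6, e = 2408.4. OR = (23.4 × 2408.4)/(396.6 × 171.6) = 0.83.

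| Assumed pattern across sites | Crude pooled OR (truth 1.00) |
|---|---|
| Only DNACPR varies, or only harm varies | 1.00 |
| Mild, aligned / reversed | 1.05 / 0.95 |
| Wide, aligned / reversed | 1.18 / 0.83 |
| Wide, one essentially unrelated ordering | 1.01 |

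**How typical are the extremes?** Over all 720 ways of pairing the wide harm rates with the wide DNACPR rates, the median OR is 1.00, the middle half runs from 0.94 to 1.06, and about 3% reach 1.15 or more.

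**Effect of adding hospital.** Logistic regression in 1000 simulated data sets per row, two-sided 5% test, no true effect:

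| Pattern | OR without site | False positives | OR with five site indicators | False positives |
|---|---|---|---|---|
| Mild, aligned | 1.05 | 6.8% | 1.00 | 4.7% |
| Wide, aligned | 1.18 | 15.6% | 1.00 | 5.1% |
| Wide, reversed | 0.81 | 10.8% | 0.98 | 4.2% |

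For the wide aligned pattern, the SD of the log odds ratio goes from 0.209 to 0.214 when site is added (0.214/0.209 = 1.02).

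**The case against.** **Silence.** Section 5.5 promises appropriate regression techniques and does not itemise the patient characteristics. An analysis plan that is not shown could add site, and matching, if done, might be on hospital. This is fair, but section 5.5 does more than stay silent. It names the independent variables of each model, and the analysis plan announced in section 4.5.1 is for the WP2 time series. Matching is conditional and is justified by power, not by control of site.

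**Size.** The larger odds ratios need site DNACPR and harm rates to rank in exactly the same or exactly the opposite order. The 720 pairings show that most orderings give little bias. The figures are also crude, and the planned adjustment would remove the part of any site difference that is due to case mix. This stands, and it limits the claim to a possible bias of unknown size and direction.

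**Mitigation and weight.** Training, standardisation across the six sites, reliability reporting and quality checks should reduce differences in recording. WP3 is descriptive and its analysis is called exploratory. Both points lower the weight. Neither puts hospital into the model, and the conclusion foreseen in section 5.3.1 is still worded causally.

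**Stronger readings to avoid.** A reader might infer that clustering of patients within wards also biases the estimate or makes its interval materially too narrow. The documents do not support this as a finding. Section 5.3 lists no ward of assessment among the data collected, clustered standard errors would not remove bias, and no figure in the protocol sizes the loss of precision. A reader might also infer a bias as large as a full standard error. With the protocol's 14% DNACPR share, even the wide aligned pattern gives log 1.18 = 0.17 against a standard error of about 0.21.

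**Conclusion.** The point holds as a gap in the specified models: hospital is a plausible confounder on the protocol's own description and is in none of the three regressions. Without it, the pooled DNACPR–harm odds ratio does not isolate the within-hospital association that research question 5 needs.

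The documents do not show that the estimate will be biased. Bias arises only if DNACPR use and harm recording both vary between hospitals and are related across them. Under the assumed spreads the crude odds ratio moves from 1.00 to between 1.05 and 1.18 when fully aligned, to between 0.95 and 0.83 when fully reversed, and stays near 1.00 when unrelated. The sizes apply to the harm model; none was worked out for the DNACPR and care-group models, where the case for a hospital term rests on the same reasoning without a number.

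**What to change.** In section 5.5, or in the WP3 analysis plan, add hospital as a fixed effect (five indicators for six sites) to the WP3 models, first of all the harm model. If cases are matched to controls, match within hospital. Report the DNACPR–harm odds ratio with and without hospital, so that readers can see how much of the association lies between sites.

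The site identifier is already held (section 5.2), so this changes the wording of the analysis and needs no new data. About 195 harms can support five more parameters. The interval becomes marginally wider, with the SD of the log odds ratio at about 0.214 instead of 0.209 in the pattern tested.
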